9.3.3 Handling of intercurrent events of primary estimand (if applicable)

Intercurrent events for the primary endpoint are defined in Section 3.1 and the strategy for handling of intercurrent events in the primary analysis is described below:

- 1) Discontinuation of study treatment: mean 24hr SBP data collected after discontinuation of study treatment will be used in the analysis (treatment policy strategy).
- 2) Unforeseen change in the dose of allowed concomitant medications: mean 24hr SBP data collected after unforeseen change in the dose of allowed concomitant medication will be used in the analysis (treatment policy strategy).
- 3) Receiving prohibited concomitant medication: mean 24hr SBP data collected after receiving prohibited concomitant medication will be used in the analysis (treatment policy strategy).

If missing data for primary endpoint occurs after intercurrent event(s), it will be imputed based on participants with observed endpoint after same type of intercurrent event(s) in the respective treatment group. If there is no or very limited participants with observed endpoint after intercurrent event(s) in the respective treatment group, then missing will be imputed based on the respective treatment group combined with lower dose group(s). If there are still very limited participants with observed endpoint after intercurrent event(s), then missing will be imputed based on those with observed endpoint in the placebo group.

9.3.4 Handling of missing values not related to intercurrent event

Missing data for the primary endpoint will be imputed using a multiple imputation approach assuming that missingness mechanism can be retrieved from observed data (missing at random (MAR)). The imputation model will include the longitudinal sequence of mean 24hr SBP data collected at baseline, Week 9 and Week 12 visits, number of background antihypertensive medications (3 or >3), region, and other baseline variables as appropriate, imputing for each treatment group separately.

The full detailed information about the multiple imputation algorithms will be specified in a separate statistical analysis plan.

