6.5.3 Dose modifications

Except for force up-titration of study medications outlined in Section 6.5.1.1, Investigational study treatment dose adjustments and/or interruptions are not permitted. Participants who are considered to be intolerant to study medications should discontinue study treatment.

Safety criteria determining dose interruption or discontinuation based on liver or renal events are listed in Appendix 5 (Section 10.5) and Appendix 6 (Section 10.6), respectively. Deviations from mandatory dose interruptions and/or reductions are not allowed.

If the participant experiences severe hypertension (defined as SBP > 180 mmHg confirmed by 3 readings 5 minutes apart), consider discontinuing all study medication and starting the subject on open label treatment accompanied by monitoring of BP as per local standard of care until the doses of the new medications are stable and BP is under control.

Dose modifications of background therapy

Dose adjustments of any component(s) of the background antihypertensive therapy medications and study medication due to hypotension are listed in Section 10.7.

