9.3.7 Supplementary analysis

The supportive analyses for the primary analysis results are listed below:

- 1. Results based on the single best dose response model fit will also be reported.
- 2. The mixed model for repeated measure (MMRM) analysis of covariance (ANCOVA) with treatment, number of background antihypertensive medications (3 or >3), region, visit (Week 9 or Week 12), and treatment-by-visit as factors, and baseline mean 24hr SBP as a covariate, with a common unstructured covariance matrix among visits will be used. Treatment comparisons at Week 12 will be provided. The analysis will be based on all available data up to Week 12 in the FAS and based on likelihood method with an assumption of missing at random for missing data.

- 3. In addition to treatment policy strategy to handle the intercurrent events in the primary analysis, a supplemental analysis based on a hypothetical strategy will be also used to handle the intercurrent events. This strategy assumes that premature discontinuations of study treatment, change in the dose of allowed concomitant medication, receiving prohibited concomitant medication or lost to follow-up/discontinue study would not have occurred in the participants. This analysis uses partial data available up to the occurrence of the intercurrent events, and missing data after the intercurrent events will be imputed as based on the pattern of other participants who do not have intercurrent events (missing at random). The imputation steps are same as described in Section 9.3.4 and the newly imputed data will be used in the analysis as described in Section 9.3.2.
- 4. Analysis based on the while on-treatment strategy to handle the intercurrent of premature discontinuations of study treatment will be performed. This analysis uses the data taken at the end of treatment visit as the Week 12 assessment and repeat the analysis described in Section 9.3.2.
- 5. Subgroup analyses will be performed for the primary analysis. The analysis will be done using the analysis specified in Section 9.3.2 at individual subgroup level separately. Please see Section 9.7 for subgroup details.

Summary statistics for mean 24hr SBP and change from baseline will be summarized by treatment group for observed and imputed values. Figures will be produced to visually show the raw and the imputed mean changes by visit over 12 weeks randomized treatment epoch for each treatment group. FAS will be used for the analyses.

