2.5.4 Handling of missing values not related to intercurrent event

Missing data for the primary endpoint will be imputed using a multiple imputation approach assuming that missingness mechanism can be retrieved from observed data (missing at random (MAR)). MIs (100) of missing Week 12 mean 24hr SBP under MAR assumption are generated, resulting in multiple imputed datasets (100). The imputation model with fully conditional

method (FCS) will include longitudinal sequence of mean 24hr SBP data collected at baseline, Week 9 and Week 12 visits, number of background antihypertensive medications (=3 vs >3), and region stratification factor (with Japan combined into Asia), imputing for each treatment group separately. SAS proc MI FCS statement is used to impute missing values in the following sequence: factor variables in the increasing order of missing frequency, the mean 24hr SBP at baseline, Week 9 and Week 12.

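### The hypothetical-strategy supplementary analysis imputes without post-baseline office SBP, so participants with an intercurrent event before Week 9 are filled in from baseline alone

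*Protocol*

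**What the plan says.** Protocol 9.3.4 assumes that values missing for reasons other than an intercurrent event are missing at random. Its model holds ABPM SBP ("The imputation model will include the longitudinal sequence of mean 24hr SBP data collected at baseline, Week 9 and Week 12 visits") and "number of background antihypertensive medications (3 or >3), region, and other baseline variables as appropriate, imputing for each treatment group separately". SAP 2.5.4 keeps the ABPM values, drug count and region, omits the other baseline variables, and fixes the method ("SAS proc MI FCS statement is used to impute missing values in the following sequence"): factors first, then ABPM at baseline, Week 9 and Week 12. Neither names a post-baseline office SBP.

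Protocol 9.3.7 item 3 (SAP 2.5.7 item 3) plans a supplementary analysis as if treatment discontinuation, background-dose change, prohibited medication and loss to follow-up had not happened. It keeps data up to the event and imputes the rest. The protocol adds: "The imputation steps are same as described in Section 9.3.4". The SAP points in the same way to its Section 2.5.4.

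Protocol 6.5.3 defines severe hypertension as "SBP > 180 mmHg confirmed by 3 readings 5 minutes apart" and links it to stopping study medication; 7.1 also lists SBP that stays above 180 mmHg. Protocol 8.3.1 schedules ABPM at the end of run-in, Week 9 and Week 12. The schedule of activities, read with 8.4.1, has blood pressure taken at the examinations at Weeks 2, 4, 8, 9 and 12.

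**The concern.** The imputation is credible only if, given what is in the model, participants with an event would have had the same Week 12 ABPM as those without one. For an event before Week 9, what is in the model is baseline ABPM, drug count and region, within arm. Yet the participant may have been stopped because a clinic reading was high, and that reading is a recorded post-baseline value related to the missing outcome.

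At stake is the estimate of the effect had nobody stopped or been rescued. If placebo participants leave with high pressure and XXB750 participants with low pressure, the former are imputed too low and the latter too high, and the difference moves toward zero. The exposed group can be wider than treatment stops: SAP 1.2.1 counts any change in background dose, including a switch within class, as an event.

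**Working it through.** **Inputs from the documents.** SD 12 mmHg and a 10 mmHg maximum effect (Protocol 9.9.1); 34 randomized per arm (Table 4-1) and 30 in the power calculation. As a check on these inputs, 30 against 30 gives 88.8% power by the noncentral t, against the stated 89% (9.9.2). The plan gives no figure of its own for the point at issue.

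**Inputs that must be assumed.**
- f, the share per arm with a BP-driven event before Week 9: 8%, or 34 × 0.08 = 2.7 participants. The documents give only about 10% lost to follow-up.
- ρ, the correlation between pre-event office SBP and the Week 12 ABPM change, given baseline: 0.3 to 0.5.
- m, how far those who stop lie from their arm's mean office SBP: 1 SD.

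**Formula.** Those who stop have a true mean ρσm away from the arm mean. Those who stay lie ρσm·f/(1−f) on the other side, and the imputation places the stoppers there. The gap is ρσm/(1−f), and it applies to a share f, so

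error in one arm = f/(1−f) × m × ρ × σ.

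With f = 0.08, m = 1 and σ = 12: 0.08/0.92 × 12 = 1.04, times ρ.
- ρ = 0.3: 0.31 mmHg per arm.
- ρ = 0.5: 0.52 mmHg per arm.

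**Effect on a true difference of 10 mmHg.**

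| Who stops early | Estimate, ρ = 0.3 | Estimate, ρ = 0.5 |
|---|---|---|
| High on placebo, low on drug | 10 − 0.63 = 9.4 | 10 − 1.04 = 9.0 |
| High on placebo only | 9.7 | 9.5 |
| High in both arms equally | 10.0 | 10.0 |
| High on drug only | 10.3 | 10.5 |

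The extreme case is that exactly the top 8% on placebo and the bottom 8% on drug stop. Then m = φ(1.405)/0.08 = 1.86, and the first row loses 2 × 0.97 = 1.9 mmHg at ρ = 0.5 and 2 × 0.58 = 1.2 mmHg at ρ = 0.3. That is a ceiling, because stopping is not decided by office SBP alone.

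**Simulation.**
- With 34 per arm, about 8% stopping with a probability that depends on Week 4 office SBP (high on placebo, low on drug) and ρ of 0.3 to 0.5, the estimate shrank by about 0.6 to 1.0 mmHg. One office SBP term removed this with no loss of precision. When ABPM was instead invalid at random, the term gained nothing.
- A separate large-sample run used a correlation of 0.6, no change in BP after stopping and no data after the stop. With high-BP stops only (7.0% placebo, 1.9% drug), the model without office SBP gave 9.43 against a true 10.01, and with it 10.02. With symptomatic low-BP stops added (7.6% and 4.3% in all), it gave 9.15 against 9.92, and with office SBP 9.92.

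**The case against.** **The primary analysis.** A reader might infer that participants stopped or rescued for BP are imputed by this model there, so that the trial's main estimate shrinks. The documents do not support that. Section 9.3.4 is limited to missingness unrelated to an intercurrent event. Treatment stops, background-dose changes and prohibited medication are intercurrent events under Protocol 3.1 and 9.3.3 and SAP 2.5.3: later ABPM is used, and gaps are filled from participants with observed data after the same kind of event, then with lower doses added, then from placebo. Stopped participants are asked to keep attending (4.1). Invalid ABPM does reach the 9.3.4 model, but nothing in the documents ties invalid recordings to BP level. This objection stands.

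**The triggers.** Only the rule at 180 mmHg acts on repeated cuff readings. Hypotension is managed on symptoms whatever the reading (10.7), and rescue is the investigator's judgement with no threshold (6.8.1). For those two, office SBP is a correlate. This stands too, and it is why the extreme case is only a ceiling.

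**The direction.** It is not fixed, as the table shows. For dropout due to adverse events or death, Protocol 9.3.6 itself expects bias in favour of XXB750.

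**Early ABPM.** Protocol 6.8.1 asks for an end-of-treatment ABPM before rescue therapy begins, and 8.3.1 brings ABPM forward after a premature stop. Such a recording could help. But the sequence has places only for baseline, Week 9 and Week 12, and neither document says where an early recording goes.

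**Overshoot.** Under treatment policy, office SBP from before a stop misses the later effect of rescue. With rescue lowering BP by 15 mmHg, adding it gave 9.97 against a true 9.21. That argues against extending the change to 9.3.3. It does not apply to the hypothetical estimand, which asks for the outcome without the event.

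**Conclusion.** The point holds for the hypothetical-strategy supplementary analysis. That analysis imputes everyone with an event before Week 9 from baseline information alone, although a recorded value that bears on some of the stopping decisions is available. Under the stated assumptions (8% per arm, opposite directions by arm, correlation 0.3 to 0.5, stoppers about 1 SD out), the cost is roughly 0.6 to 1.0 mmHg of 10. Equal high-BP stops in both arms give no bias, and high-BP stops on drug alone inflate the effect by 0.3 to 0.5 mmHg. The documents supply neither the stop rate nor the correlation, so size and sign are conditional.

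No hypothesis test rests on this analysis, and the primary analysis is largely unaffected. This is a cheap improvement to one supplementary analysis. It is not a flaw in the primary result.

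**What to change.** In SAP 2.5.7 item 3, and to match in Protocol 9.3.7 item 3, keep the steps of SAP 2.5.4 but add mean sitting office SBP at Week 4, and at Week 8 if that precedes the event, to the FCS sequence ahead of the Week 9 and Week 12 ABPM. Use these as auxiliary variables only. State that a reading counts as pre-event if it was taken before the change in therapy, so that the reading that prompted the decision is kept. Leave the ANCOVA and the retrieved-dropout imputation of 9.3.3 / SAP 2.5.3 as they are.

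The cost is one or two more coefficients per arm on about 30 participants, and no new data. Two limits remain. An event before Week 4 still has neither value. Readings at unscheduled visits stay out, because SAP 2.1.1 generally excludes them from efficacy evaluation.

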9.3.5 Multiplicity adjustment (if applicable)

Please refer to Section 9.3.2 for primary analysis of MCP-MOD for multiplicity adjustment with respect to testing for a dose response signal across multiple candidate shapes. The secondary hypotheses included in the order of hierarchical testing procedure are: (1) evaluate and demonstrate treatment effect of highest XXB750 dose group versus placebo in reducing the mean 24hr SBP from baseline to Week 12, (2), evaluate and demonstrate treatment effect of highest XXB750 dose group versus placebo in reducing the average of mean 24hr SBP from baseline to Week 9 and Week 12 and (3) dose-response relationship in terms of proportions of participants achieving BP control among XXB750 dose groups and placebo. The secondary hypotheses will be tested in the order described above and statistical inference will be made only if the primary hypothesis is rejected.

9.3.6 Sensitivity analyses

The primary analysis using retrieved dropouts or missing at random (MAR) approaches for missing values after early treatment/study discontinuation due to adverse event(s) or death may assign values in the XXB750 dose groups that are too favorable. Therefore, a sensitivity analysis will be performed where missing values after early treatment/study discontinuation due to AE or death will be multiply imputed based on results from similar patients in the placebo group. Placebo multiple imputation method will be performed, where participants randomized to XXB750 dose groups are assumed to be similar to placebo treated participants after drop-out.

9.3.7 Supplementary analysis

The supportive analyses for the primary analysis results are listed below:

- 1. Results based on the single best dose response model fit will also be reported.
- 2. The mixed model for repeated measure (MMRM) analysis of covariance (ANCOVA) with treatment, number of background antihypertensive medications (3 or >3), region, visit (Week 9 or Week 12), and treatment-by-visit as factors, and baseline mean 24hr SBP as a covariate, with a common unstructured covariance matrix among visits will be used. Treatment comparisons at Week 12 will be provided. The analysis will be based on all available data up to Week 12 in the FAS and based on likelihood method with an assumption of missing at random for missing data.

- 3. In addition to treatment policy strategy to handle the intercurrent events in the primary analysis, a supplemental analysis based on a hypothetical strategy will be also used to handle the intercurrent events. This strategy assumes that premature discontinuations of study treatment, change in the dose of allowed concomitant medication, receiving prohibited concomitant medication or lost to follow-up/discontinue study would not have occurred in the participants. This analysis uses partial data available up to the occurrence of the intercurrent events, and missing data after the intercurrent events will be imputed as based on the pattern of other participants who do not have intercurrent events (missing at random). The imputation steps are same as described in Section 9.3.4 and the newly imputed data will be used in the analysis as described in Section 9.3.2.
- 4. Analysis based on the while on-treatment strategy to handle the intercurrent of premature discontinuations of study treatment will be performed. This analysis uses the data taken at the end of treatment visit as the Week 12 assessment and repeat the analysis described in Section 9.3.2.
- 5. Subgroup analyses will be performed for the primary analysis. The analysis will be done using the analysis specified in Section 9.3.2 at individual subgroup level separately. Please see Section 9.7 for subgroup details.

Summary statistics for mean 24hr SBP and change from baseline will be summarized by treatment group for observed and imputed values. Figures will be produced to visually show the raw and the imputed mean changes by visit over 12 weeks randomized treatment epoch for each treatment group. FAS will be used for the analyses.

9.4 Secondary endpoint(s)/estimand(s) analysis

The secondary efficacy endpoints are described in Section 9.4.1 and are part of the hierarchical testing strategy. Analyses related to safety endpoints are described in Section 9.4.2.

9.4.1 Efficacy endpoints

There are three efficacy secondary objectives:

- 1. Between treatment comparison of XXB750 highest dose versus placebo in reducing the mean 24hr SBP from baseline at Week 12.
- 2. Between treatment comparison of XXB750 highest dose versus placebo in reducing the average of the mean 24hr SBP from baseline at Week 9 and at Week 12
- 3. To determine a dose-response signal and to characterize the dose-response relationship in XXB750 doses and placebo with respect to the proportion of participants achieving BP control at week 12.

The efficacy variable in secondary objective 1 is the change from baseline at Week 12 in the mean 24hr SBP and will be analyzed using a repeated measures ANCOVA model with treatment, number of background antihypertensive medications (3 or >3), region, visit (Week 9 or Week 12), and treatment-by-visit as factors, and baseline mean 24hr SBP as a covariate, with a common unstructured covariance matrix among visits. The analysis time point for the treatment comparisons is at Week 12. Please refer to Section 3.2 and Section 9.3.3 for the intercurrent events and its handling strategy and Section 9.3.4 for handling missing data not related to intercurrent event. The analysis will be run on each of the imputed datasets as

described in Section 9.3.2. Overall results are obtained by applying Rubin's rules on the estimates obtained from imputed datasets.

[figure not shown]
The efficacy variable in secondary objective 2 is the average change from baseline at Week 9 and Week 12 in the mean 24hr SBP and will be analyzed using an analysis of covariance (ANCOVA) model including treatment, number of background antihypertensive medications (3 or >3), and region as fixed-effect factors and baseline mean 24hr SBP as covariate. Within treatment and between treatment comparisons will be provided. Please refer to Section 3.2 and Section 9.3.3 for the intercurrent events and its handling strategy and Section 9.3.4 for handling missing data not related to intercurrent event. The analysis will be run on each of the imputed datasets as described in Section 9.3.2. Overall results are obtained by applying Rubin's rules on the estimates obtained from imputed datasets.

The efficacy variable in secondary objective 3 is the achievement of BP control by ABPM (i.e., mean 24hr SBP <130 mmHg and 24-hour mean ambulatory diastolic blood pressure (mean 24hr DBP) <80 mmHg) at Week 12.

There are five candidate models to capture the shape of the dose-response relationship for XXB750 with respect to the proportion of participants with BP control at Week 12, as depicted in Figure 9-2. The candidate models generating the contrast weights are described below:

- Model 1: Emax with ED50 at 30 mg SC q4w
- Model 2: Emax with ED50 at 60 mg SC q4w
- Model 3: sigmoid Emax with ED50 at 30 mg SC q4w and hill parameter h=3
- Model 4: sigmoid Emax with ED50 at 120 mg SC q4w and hill parameter h=3
- Model 5: Beta-model with delta1=0.2, delta2=0.3 and scale=288

Figure 9-2 Dose-response curve of candidate models for proportion of participants with BP control

The analysis method of generalized MCP-Mod for binary data is similar as the primary analysis described in Section 9.3.2, but with the response for participant i in treatment k, Y_{ki} , follows a Bernoulli(p_k), where p_k is the probability of participants achieving BP control in treatment group k. And logit(p_k) will be estimated using a logistic regression with treatment (placebo and XXB750 dose groups), number of background antihypertensive medications (3 or >3), and region as factors, and the baseline mean 24hr SBP and mean 24hr DBP as covariates. The intercurrent events and corresponding handling strategy are described in Section 3.2, and the handling of missing not related to intercurrent events in Section 9.3.2 and Section 9.3.4 so that achievement of BP control will be based on imputed mean 24hr SBP and mean 24hr DBP at Week 12. Participants with intercurrent events will be imputed as not having BP control in the analysis.

[figure not shown]
The statistical testing procedure described below will be carried out for the multiple treatment comparisons in the primary and secondary efficacy objectives to ensure that the overall significance level for the multiple hypotheses to be tested is controlled at the one-sided 0.025 level (i.e. two-sided 0.05).

The testing hypotheses associated with secondary efficacy objectives are described below:

- **H**₂₀: No difference in the change of mean 24hr SBP from baseline at Week 12 between highest XXB750 dose versus placebo.
- H₃₀: No difference in average change of mean 24hr SBP from baseline at Week 9 and at Week 12 between highest XXB750 dose versus placebo.
- H₄₀: There is no dose-response relationship for XXB750 (i.e. all dose groups have the same response as the placebo group) in terms of proportions of participants achieving blood pressure control at Week 12.

The testing procedure is to be based on the sequentially rejective multiple test procedure prespecified in controlling overall type I error (Bretz et al 2009) and H₁₀ of the primary hypothesis will be initially test first at the one-sided 0.025 significance level. If the primary hypothesis can be rejected, the relocation of its significance level with a weight of 1 to the other hypotheses is specified in Figure 9-3 below. The sequentially rejective multiple test procedure is completed until no more hypothesis can be further rejected.

Figure 9-3 Sequentially rejective multiple testing procedure

Number and percentage of participants with ambulatory BP control will be summarized by treatment group for observed and imputed values. Figures will be produced to visually show the raw and the imputed ambulatory BP control by visit over 12 weeks randomized treatment epoch for each treatment group. FAS will be used for the analyses.

